2.5 Analysis of the primary objective

The primary objective of the study is to assess the proportion of patients who are alive without disease progression at 6 months based on local investigator assessment per RECIST v1.1 separately in Cohorts A and C (alpelisib in combination with fulvestrant) and Cohort B (alpelisib in combination with letrozole) among patients with HR+, HER2-negative aBC harboring a PIK3CA mutation who have progressed on or after prior treatments.

2.5.1 Primary endpoint

The primary efficacy endpoint is the proportion of patients who are alive without disease progression at 6 months based on local investigator assessment using RECIST v1.1 in each cohort.

The mFAS will be used for the primary efficacy analysis.

2.5.2 Statistical hypothesis, model, and method of analysis

In post CDK 4/6 inhibitor progression setting a **CCI** response rate is considered as a clinically meaningful threshold in each cohort. Therefore, evidence of treatment effect will be tested using the following hypothesis:

$H_0: \text{CCI}$

$H_1: \text{CCI}$

Where p is the proportion of patients who are alive without progression at 6 months.

The primary endpoint will be presented together with two-sided 95% confidence intervals using Clopper and Pearson (1934) exact method for both cohorts separately. The null hypothesis will be rejected and evidence of treatment effect will be demonstrated if the lower bound of the 95% CI for observed proportion at 6 months is greater than **CCI**. **Table 2-4** displays the values of proportion of patients who are alive without any disease progression at 6 months and its 95% CI. To reject the null hypothesis **CCI** at least 44 patients need to be alive without progression at 6 months out of 112 patients in each cohort.

Table 2-4 **Exact 95% Confidence Interval**

Sample size (N)	Number of patients alive without PD at 6 months (k)	Proportion k/N (%)	Exact 95% Confidence Interval (CI)	
			Lower (%)	Upper (%)
112	CCI	CCI	CCI	CCI

2.5.3 Handling of missing values/censoring/discontinuations

Six months is defined in this study as 24 weeks \pm 1 week. Therefore tumor assessments between week 23 and 25 will be considered for the primary analysis. For primary endpoint analysis, patients who progressed, died, or discontinued study before 6 months will be counted as a “failure”.

2.5.4 Supportive analyses

The primary analysis will also be performed on the FAS and may be repeated on PPS, if hypothesis on the primary endpoint for the mFAS is met.

The primary analysis will also be repeated in patients from mFAS harboring a PIK3CA mutation as determined via ctDNA. This analysis will be conducted using the same analytical conventions as the primary analysis.

2.6 Analysis of the key secondary objective

Not applicable.

2.7 Analysis of secondary efficacy objective(s)

The secondary objectives in this study are to evaluate the progression free survival (PFS), progression free survival 2 (PFS2), overall response rate (ORR), clinical benefit rate (CBR), overall survival (OS), duration of response (DOR), and safety. For efficacy secondary objectives, 95% confidence intervals will be provided.

The secondary efficacy analyses will also be repeated in patients harboring a PIK3CA mutation as determined via ctDNA at baseline and conducted using the same analytical conventions.

2.7.1 Secondary endpoints

The mFAS will be used for the secondary efficacy analyses.

Progression free survival

Secondary endpoints include PFS, defined as the time from the date of start of treatment to the date of the first documented progression or death due to any cause. PFS will be based on local investigators review of tumor assessments and using RECIST 1.1 criteria (see Appendix 5 of the study protocol). If a patient has not progressed or died at the analysis cut-off date, PFS will be censored at the date of the last adequate tumor evaluation date before the cut-off date. PFS events documented after the initiation of new anti-neoplastic therapy (i.e. RECIST 1.1 documented disease progression or death) will be considered for the primary analysis provided tumor assessments continue after initiation of new cancer therapy. Discontinuation due to disease progression (collected on the 'End of treatment' and 'End of post treatment follow up' disposition pages) without supporting objective evidence satisfying progression criteria per RECIST 1.1 will not be considered disease progression for PFS derivation. Clinical deterioration will not be considered as a qualifying event for progression.

Overall response rate

ORR is defined as the proportion of patients with best overall response (BOR) of complete response (CR) or partial response (PR) according to RECIST 1.1 (see Appendix 5 of the study protocol). ORR will be calculated based using local investigators review of tumor assessment data in patients with measurable disease at baseline. Patients with only non-measurable disease at baseline will be part of the analysis and will be included in the numerator only if a complete response was observed. Tumor assessments performed before the start of any further antineoplastic therapy (i.e. any additional secondary antineoplastic therapy or surgery) will be considered in the assessment of BOR.

Clinical benefit rate (CBR)

CBR is defined as the proportion of patients with a best overall response of CR or PR, or an overall lesion response of stable disease (SD) lasting 24 weeks or longer or Non-CR/ Non-PD lasting 24 weeks or longer, according to RECIST 1.1 criteria. A patient will be considered to have SD for 24 weeks or longer if a SD response is recorded at 23 weeks or later from

enrollment, allowing for the +1 week visit window for tumor assessments. Patients with only non-measurable disease at baseline will be part of the analysis and will be included in the numerator only if they achieve a complete response or have a 'Non-CR/Non-PD' response 23 weeks or more after start of study treatment. CBR will be calculated using the mFAS based on the investigators' tumor assessments.

Duration of response

Duration of response (DOR) only applies to patients whose best overall response is complete response (CR) or partial response (PR) according to RECIST 1.1 based on local investigators review of tumor assessment data. The start date is the date of first documented response of CR or PR (i.e., the start date of response, not the date when response was confirmed), and the end date is defined as the date of the first documented progression or death due to underlying cancer. Patients continuing without progression or death due to underlying cancer will be censored at the date of their last adequate tumor assessment using the censoring rule described for PFS analysis (options A(1), C2(1), D(1), E(1), F(1-3) and G(1) from Table 3-2 in Appendix 5 of the study protocol).

Overall Survival

OS is defined as the time from date of start treatment to date of death due to any cause. If a patient is not known to have died, then OS will be censored at the date of last known date patient alive.

PFS after next-line of treatment (PFS2)

PFS2 is defined as time from date of start of treatment to the first documented disease progression (clinical or radiologic) on next-line therapy or death from any cause, whichever occurs first. The first documented progression on next-line treatment will be based on investigator assessment of PD (i.e. as captured on the anti-neoplastic therapy after treatment discontinuation CRF page).

1. Next-line therapy is defined as the first new (systemic) anti-neoplastic therapy initiated after discontinuation of study treatment regardless of EoT reason. Drugs given as part of the same regimen should be grouped as one line (i.e. part of the next-line therapy). In addition, continuation of the study treatment after the initial radiologic disease progression will not be considered as next-line therapy.
2. PFS2 will be censored if no PFS2 event (progression or death) is observed during next-line therapy before the analysis cut-off date; the censoring date will be the last contact date.
3. However, in case a second new anti-neoplastic therapy is introduced without prior PFS2 event, then PFS2 will be censored at the end date of the first new anti-neoplastic therapy (i.e. next line therapy).
4. PFS2 will be censored at last contact date if a patient is still ongoing on study treatment irrespective of the disease progression status or second progression while being on study treatment, or patient has discontinued study treatment but has not started next-line therapy and is still alive.

5. Any death prior to initiation of next-line therapy will be considered as an event for PFS2.
6. PFS and PFS2 may be identical if a patient did not experience an event (i.e. progression) prior to initiation of next-line therapy, and adequate tumor assessments continue until RECIST 1.1-documented disease progression after initiation of next-line therapy.

Extension Phase Clinical Benefit

The secondary objective related to the Extension Phase of the study is to evaluate clinical benefit as assessed by the Investigator. Proportion of patients with clinical benefit is defined by the number of patients with clinical benefit as assessed by investigator during Extension Phase (begins after the end of the Core Phase) divided by the number of patients in Extension Phase (Safety set in Extension Phase).

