Any potentially measurable lesion that has been previously treated with radiotherapy should be considered as a non-measurable lesion. However, if a lesion previously treated with radiotherapy has clearly progressed since the radiotherapy, it can be considered as a measurable lesion.

Each lesion that is measured at baseline must be measured by the same method (either same radiologic/nuclear method or by physical exam) throughout the study so that the comparison is consistent. Criteria required for determining partial or complete response should be present for at least 4 weeks.

Chest x-rays and ultrasound should not be used to measure tumor lesions.

Core Phase Treatment phase imaging assessments

Imaging assessments as described in Table 7-3 should be performed using the same imaging modality used at screening, irrespective of study treatment interruption or actual dosing. Imaging assessments for response evaluation will be performed every 12 weeks (+/- 7 days) during the Core Phase. The 12 week interval should be followed regardless of whether study treatment is temporarily withheld or unscheduled assessments are performed.

Additional imaging assessments may be performed at any time during the study at the investigator's discretion to support the efficacy evaluations for a subject, as necessary. Clinical suspicion of disease progression at any time requires a physical examination and imaging assessments to be performed promptly rather than waiting for the next scheduled imaging assessment.

Each lesion that is measured at screening must be measured by the same method (either same imaging method or by photography, including a metric ruler) and when possible, the same local radiologist/physician throughout the study so that the comparison is consistent. If an off-schedule imaging assessment is performed because progression is suspected, subsequent imaging assessments should be performed in accordance with the original imaging schedule.

Combined Positron Emission Tomography/Computed Tomography (PET/CT) may be used only if the CT is of similar diagnostic quality as a CT performed without PET, including the utilization of IV contrast media. At the discretion of the Investigators, FDG-PET scans may be performed to document progressive disease per RECIST v1.1 (Appendix 5).

Extension Phase

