3.1 Best overall response

The best overall response is the best response recorded from the start of the treatment until disease progression/recurrence (taking as reference for PD the smallest measurements recorded since the treatment started). In general, the patient's best response assignment will depend on the achievement of both measurement and confirmation criteria.

The best overall response will usually be determined from response assessments undertaken while on treatment. However, if any assessments occur after treatment withdrawal the protocol should specifically describe if these will be included in the determination of best overall response and/or whether these additional assessments will be required for sensitivity or supportive analyses. As a default, any assessments taken more than 30 days after the last dose of study treatment will not be included in the best overall response derivation. If any alternative cancer therapy is taken while on study any subsequent assessments would ordinarily be excluded from the best overall response determination. If response assessments taken after withdrawal from study treatment and/or alternative therapy are to be included in the main endpoint determination, then this should be described and justified in the protocol.

Where a study requires confirmation of response (PR or CR), changes in tumor measurements must be confirmed by repeat assessments that should be performed not less than 4 weeks after the criteria for response are first met.

². Once confirmed PR was achieved, all these assessments are considered PR.

³. As defined in Section 2.4

Longer intervals may also be appropriate. However, this must be clearly stated in the protocol. The main goal of confirmation of objective response is to avoid overestimating the response rate observed. In cases where confirmation of response is not feasible, it should be made clear when reporting the outcome of such studies that the responses are not confirmed.

- For non-randomized trials where response is the primary endpoint, confirmation is needed.
- -For trials intended to support accelerated approval, confirmation is needed
- For all other trials, confirmation of response may be considered optional.

The best overall response for each patient is determined from the sequence of overall (lesion) responses according to the following rules:

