- CR = at least two determinations of CR at least 4 weeks apart before progression where confirmation required or one determination of CR prior to progression where confirmation not required
- PR = at least two determinations of PR or better at least 4 weeks apart before progression (and not qualifying for a CR) where confirmation required or one determination of PR prior to progression where confirmation not required
- SD = at least one SD assessment (or better) > 6 weeks after randomization/start of treatment (and not qualifying for CR or PR).

The protocol should state if randomization or start of treatment is used as start date (baseline). This is then used in all definitions.

If a different minimum follow-up period is required to classify for best overall response='stable disease', this must be specified in the protocol.

• PD = progression ≤ 12 weeks after randomization/ start of treatment (and not qualifying for CR, PR or SD).

If PD in a different follow-up period is considered to classify for best overall response='progressive disease', this must be specified in the protocol.

The protocol should state if discontinuation due to 'Disease progression' or death due to study indication is considered PD even if this was not accompanied by documentation of PD based on tumor measurements. This depends on Phase of the study and the primary endpoint (e.g. Phase III studies in which progression-free survival is primary endpoint should consider only documented PD, whereas Phase I and II studies may consider all clinical deteriorations PD). The following sentence therefore is only applicable if this is specified in the protocol:

Patients with symptoms of rapidly progressing disease without radiologic evidence will be classified as progression only when clear evidence of clinical deterioration is documented and/or patient discontinued due to 'Disease progression' or death due to study indication.

• UNK = all other cases (i.e. not qualifying for confirmed CR or PR and without SD after more than 6 weeks or early progression within the first 12 weeks)

The time durations specified in the SD/PD/UNK definitions above are defaults based on a 6 week tumor assessment frequency. However these may be modified for specific indications which are more or less aggressive. In addition, it is envisaged that the time duration may also take into account assessment windows. E.g. if the assessment occurs every 6 weeks with a time

Page 182

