2.1 Data analysis general information

The final analysis will be performed by Novartis and/or a designated CRO. SAS version 9.4 or later software will be used to perform all data analyses and to generate tables, figures and listings.

Data included in the analysis

The analysis cut-off date for the first interim analysis of study data will be established after at least **CCI** patients receiving Alpelisib + Fulvestrant (cohort A) have at least 6 months of follow-up. The analysis cut-off date for the second interim analysis of study data will be established after at least **CCI** patients have been treated (regardless of cohort) and have at least 6 months of follow-up on study. The third IA will be performed after the Core Phase has ended.

The analysis cut-off date for the primary analysis of each cohort will be established 6 months after the last patient enrolled in that cohort has started treatment. The final analysis will be performed after LPLV of the study which include cumulative data (eg safety and clinical benefit) since the start of Core Phase for the patients who enter the Extension Phase.

All statistical analyses will be performed using all data collected in the database up to the data cutoff date. All data with an assessment date or event start date (e.g. vital sign assessment date or start date of an adverse event) prior to or on the cut-off date will be included in the analysis. Any data collected beyond the cut-off date will not be included in the analysis and will not be used for any derivations.

All events with start date before or on the cut-off date and end date after the cut-off date will be reported as 'ongoing'. The same rule will be applied to events starting before or on the cut-off date and not having documented end date. This approach applies, in particular, to adverse event and concomitant medication reports. For these events, the end date will not be imputed and therefore will not appear in the listings.

General analysis conventions

Pooling of centers: Unless specified otherwise, data from all study centers will be pooled for the analysis. Due to expected small number of patients enrolled at centers, no center effect will be assessed. Protocol deviations, number of patients in analysis populations and discontinuations from study treatment will be summarized by country.

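### The SAP's 24-week rule for clinical benefit names SD but not a better response, so a first, unconfirmed PR or CR at week 24 can score worse than SD

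*SAP*

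**What the plan says.** SAP 2.7.1 opens with the definition: "CBR is defined as the proportion of patients with a best overall response of CR or PR, or an overall lesion response of stable disease" (or Non-CR/Non-PD) that lasts 24 weeks. It then turns the duration into a record that a program can look for: "A patient will be considered to have SD for 24 weeks or longer if a SD response is recorded at 23 weeks or later". The one-week visit window is the reason given for using 23 rather than 24. Patients with only non-measurable disease have a rule of their own; they are "included in the numerator only if they achieve a complete response or have a 'Non-CR/Non-PD' response 23 weeks or more after start of study treatment".

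On confirmation, Protocol 7.2.1.1 says: "Criteria required for determining partial or complete response should be present for at least 4 weeks". The tumor assessment row of Protocol Table 7-1 also requires a confirmatory scan at least 4 weeks after a PR or CR is first seen. Where confirmation applies, Protocol Appendix 5, section 3.1, reads: "PR = at least two determinations of PR or better at least 4 weeks apart before progression". The same section defines SD as a BOR: "SD = at least one SD assessment (or better) > 6 weeks after randomization/start of treatment".

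Scans are due every 12 weeks, plus or minus 7 days (Protocol 7.2.1.1). CBR and ORR are the two efficacy endpoints listed for the first two interim analyses, each after at least 6 months of follow-up (SAP 2.14). For the cohort analyses, SAP 2.1 counts 6 months from the last patient's first dose; its sentence begins: "The analysis cut-off date for the primary analysis of each cohort will be established 6 months after the last patient enrolled in that cohort has".

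**The concern.** A rule for sustained disease control should never rank a deeper response below a shallower one. Read literally, this one can. Two patients both have SD at week 12 and both progress at week 36. One has SD at week 24 and counts as clinical benefit. The other has a PR at week 24, which is never confirmed, and does not count. The second patient is alive without progression at 6 months, and so is a success on the primary endpoint while failing CBR.

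What is at stake is the accuracy of a reported secondary rate, mainly at the early looks, and the consistency of its programming. No hypothesis test depends on it.

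**Working it through.** **1. The plan's own figure.** The documents state no figure for CBR. The only design figure is for the primary endpoint: 112 patients per cohort, rejection at 44 or more, one-sided 2.5% (SAP 2.5.2 and 3.1), with a null rate of 0.30 (Protocol summary, data analysis). Exact binomial calculation gives P(X ≥ 44 | 112, 0.30) = 0.0225 and P(X ≥ 44 | 112, 0.45) = 0.9055. The exact 95% lower limit is 30.2% for 44/112 (39.3%) and 29.4% for 43/112. The design reproduces. CBR does not enter it, so it serves here only to supply the denominator.

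**2. Classifying response sequences.** These are patients with measurable disease, with confirmation required. BOR follows Appendix 5, section 3.1. Numbers are weeks.

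| Sequence | BOR | Benefit, SAP wording | Benefit, SD or better |
|---|---|---|---|
| SD 12, SD 24, PD 36 | SD | yes | yes |
| SD 12, PR 24, cut-off | SD | **no** | yes |
| SD 12, PR 24, PD 28 | SD | **no** | yes |
| SD 12, PR 24, PD 36 | SD | **no** | yes |
| SD 12, PR 24, UNK 36, no later SD | SD | **no** | yes |
| SD 12, CR 24, PD 36 | SD | **no** | yes |
| SD 12, PR 24, SD 28, PD 36 | SD | yes | yes |
| SD 12, PR 24, SD 36, PD 48 | SD | yes | yes |
| SD 12, PR 24, PR 28 | PR | yes | yes |

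The two rows with a later SD count because of Appendix 5, section 3.1: when a single PR is followed by a reduction of less than 30% without progression, that next scan is SD. An SD at week 28 or 36 falls after week 23 and meets the rule.

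**3. Timing.** With the SAP's month of 30.4375 days (SAP 2.1.1), 6 months is 6 × 30.4375 = 182.6 days, and 182.6 / 7 = 26.1 weeks. A PR first seen at week 24 can be confirmed no earlier than week 24 + 4 = 28; one first seen at week 23, no earlier than week 27. Neither is possible by week 26.1. At a cut-off 6 months after the last patient starts, confirmation of a week-24 PR is therefore impossible for patients who started in about the last 28 − 26.1 = 1.9 weeks of enrollment. If confirmation waits for the week-36 scan, the span is 36 − 26.1 = 9.9 weeks.

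**4. Size.** Each affected patient moves a cohort rate by 1/112 = 0.89 points, always downward under the current wording. For illustration only, take 50/112 = 44.6% (exact 95% CI 35.2% to 54.3%) as the rate under the current wording. Restoring 1, 3 or 5 patients would give 45.5%, 47.3% or 49.1%. Neither the base nor the counts come from the documents.

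**The case against.** The case on the other side has several parts.

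- *Confirmation may not apply.* For trials where response is not the primary endpoint and which do not support accelerated approval, Appendix 5 says: "For all other trials, confirmation of response may be considered optional". SAP 2.7.1 does not say that BOR must be confirmed for ORR or CBR; SAP 2.7.2 says so only for duration of response. With unconfirmed BOR, one PR at week 24 would count and the problem would vanish. However, the trial-specific text in Protocol 7.2.1.1 and Table 7-1 requires confirmation, and it outranks a generic default. The SAP's silence stands as a second thing to clarify.
- *The sentence is about timing.* It sets the visit window, and a programmer might take SD to include anything better. That is possible, but the derivation then rests on the programmer's choice.
- *The SAP matches its parent text.* A reader might infer that the SAP departed from the protocol by leaving out the words in brackets in "SD = at least one SD assessment (or better) > 6 weeks after randomization/start of treatment". It did not. Those words belong to the 6-week rule for BOR. Neither protocol definition of CBR (section 10.5.1.4 and Appendix 5, section 3.1) contains them. They suggest the sponsor's convention, but they neither create a discrepancy nor repair the CBR rule.
- *Most cases resolve.* A reader might also infer that every PR that is never confirmed is lost. Step 2 shows otherwise: a later SD restores the patient. A PR not yet confirmed fails only until it is confirmed or a later SD is recorded. It is missing from ORR at the same cut-off too, so part of the early effect is ordinary data immaturity. The third interim, after the Core Phase, will have settled nearly all such cases.

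None of this rescues a week-24 PR or CR followed by PD, by unknown or missing scans with no later SD, or by cut-off.

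**Conclusion.** The point holds in a narrow form. Given confirmed BOR, the literal rule denies clinical benefit to a measurable-disease patient whose first PR or CR comes at about week 24 and is followed by PD, by unknown or missing assessments with no later SD, or by data cut-off. The same patient with SD at week 24 is credited.

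The error goes one way, understating CBR by 0.89 points per affected patient in a cohort of 112. It should be largest at the first two interims and in any CBR reported at the 6-month cohort cut-offs. A reader might want to put a percentage on the total bias, but the documents give no frequency of first responses at week 24 and none for what follows them. The number affected is unknown and may be small or zero at the end of the Core Phase.

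CBR is descriptive, so the primary test, the sample size and alpha are unaffected. This is a minor wording defect that is worth correcting.

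**What to change.** In SAP 2.7.1, change the 24-week rule so that it is met by an overall lesion response of SD or better, including a PR or CR that is not confirmed, recorded at week 23 or later, before progression and before any further antineoplastic therapy. The last condition applies to this route the limit that SAP 2.7.1 already sets for BOR. In the same section, state that a BOR of CR or PR must be confirmed for ORR and CBR.

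The rule for patients with only non-measurable disease already counts CR and needs no change on this point.

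The cost is two short edits to the SAP and one condition in the derivation program. No new data are needed. If CBR has already been reported at an early cut-off under the literal rule, a count of reclassified patients per cohort would show whether it mattered.
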